Date: December 20, 2016

Principal Investigator: [name]

Application Number: IRB00081746 (IND # 128487 – IND Sponsor: [name])

Study Title: Safety, Efficacy, and Feasibility of High-dose Cholecalciferol in Pediatric Patients with Cystic Fibrosis

Principal Investigator: [name]

Application Number: IRB00081746 (IND # 128487 – IND Sponsor: [name])

Document: Protocol to accompany reported study results

NCT02613884

Date: December 20, 2016

Principal Investigator: [name]

Application Number: IRB00081746 (IND # 128487 – IND Sponsor: [name])

JHM IRB - eForm A – Protocol

Safety, Efficacy, and Feasibility of High-dose Cholecalciferol in Pediatric Patients with Cystic Fibrosis

1. Abstract

Children and adults with Cystic Fibrosis (CF) are at risk of developing a vitamin D deficiency or insufficiency, defined as a 25-hydroxyvitamin D (25OHD) serum blood level <30 ng/mL. Greater than 85% of people with CF have pancreatic insufficiency, which contributes to poor absorption of fat soluble vitamins and dietary fats. A 25OHD level greater than 30 ng/mL has been shown to provide improvements to markers of inflammation in adults with CF and is known to improve bone mineral density and prevent bone fractures in all populations, including CF. This study will assess the safety of a one-time high dose of cholecalciferol or vitamin D3 along with efficacy and feasibility of providing this therapy.

Children between the ages of 3 years and 18 years (inclusive), with a 25OHD level <30 ng/mL will be provided with a vitamin D3 supplement of 250,000 international units (IU) observed in our CF clinic. We hypothesize that this one-time, oral, high dose of vitamin D3 will safely and effectively raise the 25OHD level to above 30 ng/mL.

Safety will be monitored using a tiered safety protocol. Within the first tier, a serum calcium level and a serum phosphorus level will be measured at 1 week and 3 months following the dosage. This timing is appropriate as cholecalciferol has a half-life of 2-3 weeks and these timed levels would be at or near the middle of the 25-OHD range. A second tier safety evaluation will only be done if serum calcium levels or serum phosphorus levels are elevated. For this second tier, the participant will have a parathyroid hormone level measured (PTH) as well as a spot urine calcium to creatinine ratio.

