The following safety measures have been reviewed and approved by two Johns Hopkins All Children's Hospital Endocrinologists: As additional measures of safety at 7 days to the next working business day of the administration of the 250,000 IU of vitamin D3, all participants will also have a serum calcium and serum phosphorus level measured. If any participant has a serum calcium above the upper limits of normal (ULN) for their age (appendix B), they will be contacted via telephone to be queried about symptoms of hypercalcemia such as muscle weakness, confusion, vomiting, anorexia, confusion, polyuria and polydipsia. If the patient has more than 1 symptom of hypercalcemia and an elevated serum calcium level, we will consider this an adverse event. During this communication, it will be decided if any type of treatment will be needed to remedy the complaint (see section on treatment of hypervitaminosis D from hypercalcemia).

If any participant has a serum calcium level greater than the ULN for age or a serum phosphorus level greater than the ULN for age, a second tier of safety measures will be taken. This will include measuring a PTH with reflex calcium level as soon as possible, within approximately 7 days (± 3 days) of the serum calcium or phosphorus lab draw. In addition, we will obtain a spot urine calcium to creatinine ratio. Calcium levels and/or phosphorus levels will be repeated every 2 weeks (+7 days) until normalized for age. If the spot urine calcium to creatinine ratio is $> ULN$ for age (Appendix C) we will obtain an Endocrinology consult and if symptomatic be instructed to go to the Johns Hopkins All Children's Hospital for evaluation. The urine calcium to creatinine ratio will be repeated in 1 week (+3 days) and then monthly (+7 days) until normalized for age. Proposed treatment for hyperphosphatemia will involve increased fluids and restriction of phosphorus loaded foods. Proposed treatment for hypercalcemia, as reflected by a serum calcium level, is detailed in another section of this protocol.

To evaluate for feasibility, at 7 days to the next working business day after administration of the 250,000 IU administration of Vitamin D3, participants will be contacted by a member of the study team via phone to answer a 10-item questionnaire which is included as an appendix at the end of this protocol. This questionnaire is to assess feasibility of the 250,000 IU Vitamin D3.

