Regardless of serum calcium level or other labs collected, if a participant does become ill after taking the high dose of vitamin D3 (e.g., muscle weakness, confusion, vomiting, anorexia, polyuria and polydipsia, etc.) they will be asked to call the CF office number, [contact]. During this communication, it will be decided if any type of treatment will be needed to remedy the complaint (see section on treatment of hypervitaminosis D from hypercalcemia). If their serum calcium level was within normal limits for age, but they have symptoms of those found with hypercalcemia, it will be noted in our study findings but not classified as an adverse event.

At 12 weeks (± 30 days) from the initial study visit, participants will be required to have another 25OHD level measured via venipuncture as a part of standard of care. In addition, as a part of the

Date: December 20, 2016

Principal Investigator: [name]

Application Number: IRB00081746 (IND # 128487 – IND Sponsor: [name])

first tier of safety measures, a serum calcium and serum phosphorus level will be measured again. If either of these levels is elevated, a PTH level will be measured as soon as possible within approximately 14 days (\pm 3 days) of this serum calcium lab draw. If serum calcium level is above ULN a spot urine calcium to creatinine ratio will be ordered. At 26 weeks (\pm 30 days) and 52 weeks (\pm 30 days) the participants will have 25OHD levels measured again. No additional one-time high dosage of vitamin D3 will be prescribed or provided during the study period for any reason to any of the participants. No additional measures of safety, in the forms of serum calcium labs, serum phosphorus, or PTH will be measured.

Any participant with an elevated serum calcium level of anything above normal limits for age will be instructed to limit calcium containing foods in their diet, stop supplements with additional vitamin D and/or calcium. Since these participants will be called regarding their elevated serum calcium level to query about symptoms of hypercalcemia, we will be able to instruct them on this.

If at any time after the study intervention has started and the participant has a 25OHD level less than 30 ng/mL, they will be placed on the current standard CF Foundation step-wise guidelines for treatment appropriate for their low vitamin D level.

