There will not be a placebo group, as the study design does not support this; providing a placebo is not ethical in this population for this condition.

If a patient does not complete the study for any reason, meaning they do not get each set of lab work completed, their results up to that point in time will still be used in the study but their duration of participation will be noted in the results section. Every effort will be made to contact patients who are lost to follow up to ascertain the reason for withdrawal.

Date: December 20, 2016

Principal Investigator: [name]

Application Number: IRB00081746 (IND # 128487 – IND Sponsor: [name])

| Study Procedures | Study Time-points | | | | | | | |
|---|---------------------------|---------------|---------------------|---|------------------------------|--|---------------------------|------------------------|
| | Screening/ Eligibility | Base- line | Week 1 +/- 3 day | Week 1 B.*** Week 1+/- 14 days | Week 12 +/- 30 days | Week 12 B.*** Week 12 +/- 42 days | Week 26 +/- 30 days | Week 52 +/- 30 days |
| Informed Consent | X | | | | | | | |
| 25OHD Lab | X | | | | X | | X | X |
| Screening / Eligibility Verification (including pregnancy test) | X | | | | | | | |
| Eligibility screening: Spot Urine Calcium to Creatinine Ratio | X | | | | | | | |
| Study Registration | | X | | | | | | |
| Medication Review* | | X | | | X | | X | X |
| STOSS Vitamin D3 Administration | | X | | | | | | |
| Serum Calcium Test & Hypercalcemia Monitoring | | | X | X | X | X | | |
| Serum Phosphorus | X | | X | X | X | X | | |
| Parathyroid Hormone (PTH) Level (2 nd tier only) | | | | X | | X | | |
| Spot Urine Calcium to Creatinine Ratio (2 nd tier only) | | | | X | | X | | |
| Administration of Appendix A Questionnaire | | | X | | | | | |
| Adverse Event Assessment** | | X | X | X | X | X | X | X |

* Medication review will consist of surveying the patient's current daily maintenance dosage for vitamin D as previously prescribed.

** AEs and SAEs are defined per 21CFR312.32. All adverse events will be monitored and processed from study start until 30 days after study product administration. All adverse events deemed related to known vitamin D supplementation risks and/or study procedures will be monitored for 12 months post drug administration.

Date: December 20, 2016

Principal Investigator: [name]

Application Number: IRB00081746 (IND # 128487 – IND Sponsor: [name])

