*** 2nd tier safety assessment using PTH will only be performed in the event serum calcium levels or serum phosphorus levels are elevated greater than the upper limit of normal for age. A spot urine calcium to creatinine ratio will be done. Repeat calcium and phosphorus will be provided every 2 weeks until normalized.

5. Inclusion/Exclusion Criteria:

1. Exclusion Criteria:

- a. Any history of kidney disease, kidney stones, or on dialysis
 - b. Any history of hypercalcemia above upper limits of normal for age within the last six months (see appendix B for normal calcium levels).
 - c. Elevated serum phosphorus level at screening
 - d. Elevated spot urine calcium to creatinine ratio at screening
 - e. Abnormal serum creatinine level 2 times the upper limit of normal for age within the last 6 months
 - f. History of unresolved, abnormal liver function (ALT or AST > 4 times upper limit of normal (ULN)) or any history of portal hypertension.
 - g. Pregnant or breast feeding adolescent females; upon enrollment, will test urine sample for pregnancy in females 8 years and older
 - h. Any history of parathyroid disorders
 - i. Inability to swallow pills by mouth
- ### 2. Inclusion Criteria:
- a. Children with Cystic Fibrosis \geq 36 months of age
 - b. Serum/blood 25OHD level < 30 ng/mL
 - c. Ability to provide valid informed consent to be a part of the study
 - d. Negative urine pregnancy test upon enrollment

6. Drugs/ Substances/ Devices

This trial is being conducted under Investigational New Drug (IND) application # 128487 – IND Sponsor: [name]; all relevant FDA regulations will be followed.

Cholecalciferol (Vitamin D3) capsules from Biotechpharmaceutical will be used. Each capsule has 50,000 International Units of Vitamin D3. Each participant will be provided with 250,000 IU Vitamin D3 (5 capsules) regardless of age, sex or 25OHD level.

The dosage of 250,000 IU Vitamin D3 has been shown to be safe and effective in raising the 25OHD level in adult patients with CF and dosages higher than this have been shown to be safe and effective at raising 25OHD levels in pediatric patients as young as 36 months old with dosages of 100,000 IU Vitamin D3 in addition to pediatric patients 12 years old receiving 400,000 IU Vitamin D3 as a one-time dosage without any adverse events, including hypercalcemia.

The safety of high dose of Vitamin D3 has not been evaluated in pediatric CF patients in the U.S.

7. Off-Treatment and Off-Study Criteria

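### At week 12 the procedures text names only raised calcium as the trigger for the urine calcium to creatinine ratio, while the abstract and study calendar also trigger it on raised phosphorus

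*Combined protocol and SAP*

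**What the plan says.** The abstract (Section 1) sets first-tier calcium and phosphorus at 1 week and 3 months, and then states the condition for going further: "A second tier safety evaluation will only be done if serum calcium levels or serum phosphorus levels are elevated". It also lists what the second tier contains: "For this second tier, the participant will have a parathyroid hormone level measured (PTH) as well as a spot urine calcium to creatinine ratio".

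In Section 4, the week-1 text uses the same either-analyte trigger: "or a serum phosphorus level greater than the ULN for age, a second tier of safety measures will be taken". The week-12 text treats the two second-tier tests differently. For PTH it says "If either of these levels is elevated, a PTH level will be measured as soon as possible". For the urine test it says "If serum calcium level is above ULN a spot urine calcium to creatinine ratio will be ordered".

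The study calendar at the end of Section 4 has the row "Spot Urine Calcium to Creatinine Ratio (2 nd tier only", marked at Week 1 B and Week 12 B. Both columns carry the *** footnote, part of which reads "serum phosphorus levels are elevated greater than the upper limit of normal for age. A spot urine calcium to creatinine ratio will be done".

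Two other places name calcium alone as the reason for the urine test and are not limited to one visit: item d of the risk-minimization steps in Section 10, and the laboratory costs in Section 12.

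**The concern.** A safety rule should give the same instruction wherever staff look it up. Here the test ordered at week 12 depends on whether they work from the narrative or from the calendar. The move from either level (for PTH) to calcium (for the urine test) in consecutive sentences looks like a deliberate narrowing, so staff following the narrative would reasonably not order the ratio for raised phosphorus alone.

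The ratio feeds a later decision. Early Stopping Rule 1 in Section 9 gives a ratio above 2 times the upper limit of normal (ULN) as an alternative to serum calcium above 13.5 mg/dL. A participant meeting it may stop the study and must be treated. With no ratio measured, that criterion cannot be assessed.

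Week 12 is also the last scheduled visit with calcium and phosphorus. Section 4 measures only 25OHD at weeks 26 and 52, so no later routine laboratory result would prompt the test. Safety is the trial's primary objective, which makes a small gap of this kind worth closing.

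**Working it through.** There is no sample size, power or event figure to reproduce. The check sets the rules side by side and then works through the thresholds and cost.

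**1. Trigger by place**

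| Place | Time covered | PTH trigger | Urine-ratio trigger |
|---|---|---|---|
| Section 1, abstract | 1 week and 3 months | calcium or phosphorus | calcium or phosphorus |
| Section 4, week-1 text | 1 week | calcium or phosphorus | calcium or phosphorus |
| Section 4, week-12 text | week 12 | calcium or phosphorus | calcium named, phosphorus not |
| Section 4, calendar row with *** footnote | Week 1 B and Week 12 B | calcium or phosphorus | calcium or phosphorus, through the second-tier label and the footnote |
| Section 10, item d | not limited | not stated | calcium named, phosphorus not |
| Section 12, costs | not limited | not stated | calcium named, phosphorus not |

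**2. The possible results at week 12**

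- Both normal: neither rule orders a second-tier test.
- Calcium raised, phosphorus normal or raised: both rules order PTH and the ratio.
- Phosphorus raised, calcium normal: the abstract and calendar order PTH and 1 ratio. The week-12 text orders PTH and 0 ratios.

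The rules differ only in the last case, by one urine test per child.

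**3. What that child receives under the week-12 text**

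- PTH, from the same paragraph.
- Repeat calcium and phosphorus every 2 weeks until normal, from the *** footnote.
- Prompt notification of the principal investigator, who decides on further testing or referral, from Section 10, item d, which covers hyperphosphatemia.

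Only the automatic urine ratio is absent.

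**4. Thresholds that cannot be checked without a ratio**

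Appendix C gives a ULN of 0.42 from 19 months to 6 years and 0.22 above 6 years.

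- Stopping criterion, above 2 × ULN: 2 × 0.42 = 0.84, and 2 × 0.22 = 0.44.
- Consult criterion, above ULN: 0.42 or 0.22. Its action is "we will obtain an Endocrinology consult". It stands in the week-1 text, so its use at week 12 is an assumption.

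**5. Cost**

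- Section 12's safety budget reproduces: 3 participants × 2 time points × $73.52 = 6 × $73.52 = $441.12.
- The 3 is 10% × 30, taken from the hypercalcemia hold. That hold puts no ceiling on phosphorus-only tests.
- One added ratio: $73.52 / $441.12 = 1/6 of the budget.
- If the ratio is raised, the week-1 repeat schedule is assumed to apply, and one monthly repeat is enough: 3 × $73.52 = $220.56, half the budget. With two monthly repeats: 4 × $73.52 = $294.08.

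With k affected children, the two rules differ by k initial ratios, or k × $73.52. The documents give no value for k.

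**The case against.** The strongest defense is that all the texts can be followed together. The calcium-only sentences say what happens when calcium is raised, and none says that the ratio is for raised calcium only. Staff who order it after raised phosphorus breach nothing. This stands as logic: it is one trigger stated at two widths, and no sentence forbids the test. But if either analyte were meant to govern both tests, the second sentence would need no condition of its own, so the narrower reading is the natural one.

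The calendar evidence is also less direct than the abstract's. The row states no trigger, and the footnote attaches its condition to PTH before adding the urine test in a separate sentence. That is fair. The either-analyte reading there rests on the second-tier label together with the footnote. The abstract covers 3 months explicitly and agrees with it.

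A calcium-only urine test at week 12 may be intended, since three places name calcium alone. The documents do not settle this. If it is intended, the abstract and footnote need correcting instead.

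A reader might infer that a child with isolated raised phosphorus gets PTH and nothing more. The documents do not support that, because the repeat labs and investigator review apply. A reader might also infer that a required endocrinology consult is lost. The consult and ratio-repeat rules appear only in the week-1 text, and neither the week-12 text nor the footnote carries them forward. Finally, Sections 10 and 12 might be read as contradicting the week-1 rule. They are narrower than it, and Section 12 is cost text, so it is weak evidence of what the safety rule is.

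**Conclusion.** The inconsistency is real and lies within current text. At week 12 the procedures narrative gives a narrower trigger for the urine ratio than the abstract and calendar do. The consequence is one automatic test missing per child with isolated raised phosphorus, and with it the means to check the ratio criterion in the stopping rules. Access to care is not lost, because the investigator can still order the test.

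The size in participants is unknown. No rate of isolated raised phosphorus, or of a raised ratio in such children, is given. Only 30 children are planned, and those with raised phosphorus or a raised ratio at screening are excluded, which narrows the group.

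The conclusion assumes that the week-12 sentence is read as limiting the test to raised calcium. Any effect on consults further assumes that the week-1 consult rule is meant to carry over. The week-1 serum calcium endpoint, the sample size and the planned analyses are untouched. This is a minor correction to a safety rule, but worth making.

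**What to change.** - **Section 4, week-12 text:** replace the calcium-only sentence with: *If either level is above ULN for age, the spot urine ratio will be obtained.*
- **Section 10, item d, and the urine-test paragraph in Section 12:** change the trigger to calcium or phosphorus above ULN for age.
- **Section 12 budget:** either add an allowance for phosphorus-only tests at $73.52 each, or state that the $441.12 covers hypercalcemia-triggered tests only. Relabeling the same sum to cover both would not be enough, because its 3 participants come from the hypercalcemia hold.
- **Data Safety Monitoring Board hold:** leave it on hypercalcemia.

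The either-analyte rule is preferred because the abstract, the week-1 text and the calendar with its footnote already carry it. If the sponsor wants calcium only at week 12, the abstract and the *** footnote should say so instead.

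The cost is one sentence, two changed phrases and a budget line. No endpoint, scheduled visit or blood draw is added, since raised phosphorus already leads to PTH at Week 12 B. Each affected child adds one urine test at $73.52, plus repeats at the same price if the ratio is raised and the week-1 repeat schedule is applied.

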Research has displayed that the human body's response to vitamin D3 is biphasic, meaning it responds rapidly to low vitamin D3 doses and responds much slower to a larger vitamin D3 dose. Heaney et al. found that the low doses of vitamin D3 had a half-life of 20-30 days, but a high dose, such as 100,000 IU vitamin D3 had a half-life of 50 days (10). The authors hypothesized that perhaps at this higher dosage the vitamin D3 is being stored in fat and other body tissues and then slowly released; whereas the daily low doses of vitamin D3 provide an immediate increase or response that can sometimes be reflected in the blood sample.

In children and adults without malabsorption disorders, the current recommended range of daily vitamin D intake ranges from 400 IU per day for children as recommended by the American Academy of Pediatrics (11). Whereas the Institute of Medicine or IOM recommends a range of 600 IU to 4000 IU per day based on the age of the child. The IOM committee did increase its "upper level intake". That dose is 4,000 IU/day for adults, 3,000 IU/day for kids aged 4-8, 2,500 IU/day for kids aged 1-3, 1,500 IU/day for infants aged 6-12 months, and 1,000 IU/day for infants aged 0-6 months. The Endocrine Society for Patients at risk for vitamin D deficiency recommend a daily requirement of 400 IU-1000 IU for children depending on age and their upper level intake is 2000-4000 IU per day depending on age as well (12, 13). However, these recommendations are not for children with absorption disorders such as Cystic Fibrosis.

According to the National Institutes of Health, 25-OHD levels which are consistently greater than 200 ng/mL are "potentially toxic" (13). The IOM committee found no conclusive evidence that increased vitamin D levels confer increased health benefits, challenging the concept that "more is better". However, this was meant to be applied to healthy populations. A review of literature conducted in 2013 displayed that intoxication from vitamin D supplementation was rare in the pediatric setting. This same review also found that hypervitaminosis was "usually asymptomatic" and errors in formulation of the vitamin, manufacturing or prescription of the vitamin resulted in intoxication (13).

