1. Off-Treatment Criteria: Any patient who requires high dose supplemental vitamin D prescribed outside the study.
2. Off-Study Criteria:
 - a. Refusal of further study follow-up by patient or legal guardian

Date: December 20, 2016

Principal Investigator: [name]

Application Number: IRB00081746 (IND # 128487 – IND Sponsor: [name])

- b. Lost to follow-up
- c. Death
- d. Completion of study requirements

8. Reporting Mechanisms

1. Study Registration

- a. All patients will be registered by the Research Coordinator. The following forms will be completed: Eligibility checklist, On-study form, and Concomitant information form.

2. Toxicity and /or Adverse Reactions

- a. All adverse events will be monitored and processed from study start until 30 days after study product administration.
- b. All adverse events deemed related to known vitamin D supplementation risks and/or study procedures will be monitored for 12 months post drug administration. Serious adverse events will be defined by the criteria specified in 21CFR312.32.
- c. All safety-related event meeting FDA's expedited or annual reporting requirements as stated in 21 CFR 312.32 and 21 CFR 312.33, respectively, will be reported to the FDA.
- d. All safety-related events meeting the IRB's reporting requirements will be submitted to the IRB.

3. Informed Consent

- a. All patients and/or their legal guardian must sign a document of informed consent consistent with local institutional and federal guidelines stating that they are aware of the investigational nature of this protocol and of the possible side effects of treatment. Further, patients must be informed that no efficacy of this therapy is guaranteed and that unforeseen toxicities may occur. Patients have the right to withdraw from this protocol at any time. No patient will be accepted for treatment without such a document signed by him or his legal guardian. Full confidentiality of patients and patient records will be provided according to institutional guidelines.

4. Clinical Trial Oversight and Monitoring

- a. This protocol will be monitored and evaluated in accordance with Johns Hopkins All Children's Hospital CTRO's quality assurance procedures.

9. Statistical Analysis

The primary safety endpoint will be serum calcium levels one-week after administration of the high dose of vitamin D3. Other variables related to safety include the frequency and severity of adverse events and early stopping rules.

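### All-cause adverse events are collected only to day 30, so a later event of a new kind, even a serious one, need not enter the adverse event data

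*Combined protocol and SAP*

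**What the plan says.** Section 8, item 2a: "All adverse events will be monitored and processed from study start until 30 days after study product administration". Item 2b: "All adverse events deemed related to known vitamin D supplementation risks and/or study procedures will be monitored for 12 months post drug administration". The footnote to the "Adverse Event Assessment" row of the Section 4 calendar repeats both rules. Neither place makes an exception for serious events. Items 2c and 2d add that events meeting FDA or IRB reporting requirements will be reported, with no end date.

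The calendar marks adverse event assessment for everyone at baseline, week 1, week 12, week 26 and week 52. Two further columns, Week 1 B and Week 12 B, apply only to participants whose calcium or phosphorus is elevated. Section 4 asks families to telephone the clinic if the child becomes ill. It also states that symptoms of hypercalcemia with a normal calcium are noted but not counted as an adverse event, and that no calcium, phosphorus or PTH is scheduled after week 12.

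Section 9 names the frequency and severity of adverse events among the safety variables. It plans counts and percentages for all events and for study-related events, without giving a period for either.

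**The concern.** Safety is the only primary objective in Section 2. After day 30, a judgement of relatedness decides whether an event has to be collected at all, and that judgement is tied to risks that are already known. A harm nobody expected fails the test by its wording, unless someone attributes it to a study procedure. Yet Section 6 says "The safety of high dose of Vitamin D3 has not been evaluated in pediatric CF patients in the U.S", and the consent item in Section 8 tells families that "unforeseen toxicities may occur".

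With no control group, relatedness can only be judged case by case. After week 12 that judgement would also be made without scheduled calcium values, although Section 10 lists hypercalcemia and renal stones as risks at 6 and 12 months. If unrelated-looking events are not recorded, neither the DSMB nor the final analysis can look for a pattern among them. The safety summary could then understate late harm.

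**Working it through.** The plan gives no calculation on this point, so there is none to reproduce. The inputs are the calendar windows and text of Section 4, the rules in Section 8, item 2, the half-lives in Sections 1 and 3, and the sample size of 30 in Section 9. The day of dosing is day 0.

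**1. Contacts around the day-30 cut-off**

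- Week 1 by the calendar: 7 ± 3, so days 4 to 10. The text is tighter: "at 7 days to the next working business day of the administration of the 250,000 IU of vitamin D3".
- Week 12: 84 ± 30, so days 54 to 114.
- Gap between routine contacts: 54 − 10 = 44 days at the shortest, 84 − 7 = 77 nominally, 114 − 4 = 110 at the longest.
- Days 11 to 30 are 20 of the 30 all-cause days (20/30 = 67%) and fall after the latest permitted week-1 contact.
- An event on day 11 is first asked about 54 − 11 = 43 to 114 − 11 = 103 days later. For an event on day 30 the delay is 54 − 30 = 24 to 114 − 30 = 84 days.

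This gap holds for participants with normal week-1 calcium and phosphorus. The others have Week 1 B, which runs to day 7 + 14 = 21, and repeat tests about every two weeks until values are normal.

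**2. Follow-up without all-cause collection**

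(365 − 30)/365 = 92% of the 12 months.

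**3. Exposure when the window closes**

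Assume simple exponential decline, so the fraction remaining is 0.5^(t/h). Section 3 reports that "a high dose, such as 100,000 IU vitamin D3 had a half-life of 50 days" and gives 20–30 days for low doses. Section 1 gives 2–3 weeks and uses that figure to justify the timing of the safety tests.

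| Half-life h (days) | Source | Day 30 | Day 84 |
|---|---|---|---|
| 50 | Section 3, high dose | 66% | 31% |
| 30 | Section 3, low dose | 50% | 14% |
| 20 | Section 3, low dose | 35% | 5% |
| 21 | Section 1 | 37% | 6% |
| 14 | Section 1 | 23% | 2% |

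**4. What the rule requires after day 30**

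| Event after day 30 | Collection under items 2a–b |
|---|---|
| Attributed to a known vitamin D risk | Yes, to 12 months |
| Attributed to a study procedure | Yes, to 12 months |
| New kind, not serious, not attributed to a procedure | Not required |
| New kind, serious, not attributed to a procedure | Not required; reported to FDA or IRB if it comes to light and meets their criteria |

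**5. Illustration of the loss**

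The documents give no risk for an unexpected harm, so the 12-month risk p is an assumption. The chance of at least one recorded case among 30 children is 1 − (1 − p)^30.

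- p = 5%, every case collected: 1 − 0.95^30 = 79%.
- p = 5%, half the cases arise after day 30 and go unrecorded: 1 − 0.975^30 = 53%.
- p = 5%, three quarters do: 1 − 0.9875^30 = 31%.
- With half unrecorded, the chance falls from 26% to 14% at p = 1%, and from 96% to 79% at p = 10%.

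**The case against.** A fair defence has five parts.

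- **The known late risks are covered.** Hypercalcemia, hypervitaminosis D and renal stones judged related are kept to 12 months, and calcium and phosphorus are repeated in everyone at week 12. This stands. A reader might infer that late harms in general are filtered out, but the text supports that only for late events not attributed to known risks or procedures.
- **Serious events have another route.** Items 2c–d carry no end date and no condition that the risk be known. A reader might infer that an unrelated-looking serious event after day 30 can never be captured; these clauses contradict that. They are reporting duties, however, and do not make anyone ask about such events or enter them in the data.
- **Contact is not absent.** Families are asked to call, and participants with elevated values are followed closely. A reader might infer that nobody is seen between day 10 and day 54, but that is true only of scheduled contact for participants with normal week-1 values. The call is passive reporting.
- **The half-life argument is soft.** That most of the dose is still present at day 30 follows only from the 50-day figure, which is given for 100,000 IU. Residual drug also does not by itself show residual unexpected harm. Both points stand. The argument needs only that exposure continues past day 30, which every stated half-life gives.
- **Context.** Section 6 also cites safe use in adults with CF and in other children, the remark about unforeseen toxicity is consent wording, and a longer listing in CF patients will gather background illness. This lowers the stakes. It does not explain why relatedness should be a condition of entry.

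It might also be inferred that unrecorded events could never be re-examined. The text does not say that unrelated events are discarded; it only fails to require that they be kept.

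**Conclusion.** The point holds in a limited form. For about 92% of the follow-up year the plan does not require all-cause collection, and by its wording the rule lets a late event of a new kind, including a serious one, stay out of the adverse event data unless it is attributed to a study procedure. The window closes at a day that matches no assessment for participants with normal week-1 calcium and phosphorus, so their events on days 11–30 depend on a family call or on being recalled later. The Section 9 summary of all adverse events, read as the data would be collected, adds a 30-day all-cause count to a later related-only count running to 12 months.

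The exposure figures rest on simple exponential decline, and the detection figures on assumed risks. The reading of the rule and the day counts need neither. The week-1 calcium endpoint and the sample size are unaffected. This is a worthwhile correction to the supporting evidence for the primary objective, and it does not invalidate the design.

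**What to change.** In Section 8, item 2, and the calendar footnote:

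- collect all adverse events, regardless of relatedness, through the week-12 assessment;
- collect all serious adverse events of any cause through week 52;
- use the assessments already marked at weeks 12, 26 and 52;
- record relatedness as a separate field for each event, not as a condition for entry.

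In Section 9, tabulate all events and related events over the same stated periods. Reconcile the half-lives given in Sections 1 and 3.

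The cost is a change of wording and more background CF events in the listing, which the relatedness field can separate. No visit is added.

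Two limits should be acknowledged. Week 12 is proposed because it is the next assessment already scheduled for everyone, not because exposure has ended by then: by the table above, 2% to 31% remains at day 84. And because no contact is added, the recall delay for days 11–30 stays as it is.
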